#### 8 STATISTICAL ANALYSIS AND METHODOLOGY

#### 8.1 STATISTICAL METHODS

The investigator will collect data from the enrolled patients in an electronic Case Report Form specially designed for this study.

The patient number we provide is a serial number devoid of any identifying value.

The information is stored in an Access database, which in turn is associated with a file, "WorkGroup", detailing the user code and permits of the investigator within the database. People not within this working group cannot access the database.

A Data Management Plan (DMP) will be developed and once approved by the person responsible for the study, the "Queries" will be programmed in the electronic case form so that when the investigator saves the data, it informs him/her of any doubts regarding the data.

All changes made by the investigators during the collection of data will be stored in a table specially designed for this purpose, indicating the user, date, modified field, the old value and the new value.

The fatigue-related quality of life of the patients and the quality of life of patients with palmar-plantar erythrodysaesthesia (hand-foot syndrome) will be studied using the mean, standard deviation and confidence intervals if they follow normal distribution, or the median, minimum, maximum and interquartile range if they do not follow Gaussian distribution. The Wilcoxon test will be used to analyse the inter-visit correlation for patients' quality of life.

The objective response rate according to RECIST version 1.1 will be studied using absolute and relative frequencies.

In order to study the impact of drug administration time, napping, temporary interruptions and dose reductions on fatigue and hand-foot syndrome control, independent samples will be compared using Pearson's chi-square test (or Fisher's exact test for 2x2 tables or likelihood ratio test for mxm tables, if necessary) in the case of qualitative variables and Student's t-test, one-way ANOVA test or non-parametric equivalents, such as the Mann-Whitney U test or Kruskal-Wallis H test in the case of quantitative variables.

The Kaplan-Meier survival estimate will be used to study both the PFS and TTF of patients. The log-rank test will be used to compare the survival distributions.

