## 8.2.3 Follow-up analysis

The evolution of the following aspects will be presented for each one of the follow-up visits of the patients at which the variables listed below are recorded:

- Presence of palmar-plantar erythrodysesthesia: the absolute and relative frequency of patients who as of month 3 of treatment develop palmar-plantar erythrodysesthesia of any grade will be provided. In the sub-population of patients with hand-foot syndrome, the frequency distribution will be presented according to the degree of severity of these AE, according to CTCAE (Common Terminology Criteria form Adverse Event) version 4:
  - o Grade 1
  - o Grade 2

#### o Grade 3

For each one of the evolution visits (month 6 and month 9), a study will be performed to ascertain whether significant changes have occurred in the presence and the grade of the HFS with regard to the previous visit, defined as (improved, maintained or worsened). The Pearson chi-squared test will be used for this purpose (or Fisher's exact test for 2x2 tables or likelihood ratio test for mxn tables, if necessary).

- Presence of fatigue: the absolute and relative frequency of patients with the presence of fatigue of any degree since the baseline visit will be provided. In the sub-population of patients with fatigue, the frequency distribution will be presented according to the degree of severity, according to CTCAE (Common Terminology Criteria form Adverse Event) version 4:
  - o Grade 1
  - o Grade 2
  - o Grade 3
  - o Grade 4

For each one of the evolution visits (month 3, month 6 and month 9), a study will be performed to ascertain whether significant changes have occurred in the grade of fatigue with regard to the previous visit, defined as (improved, maintained or worsened). Significant associations will be sought between the habits of daytime rest, physical aerobic exercise, medication taken, dose and treatment schedule changes, dose interruptions and the number of days of treatment interruption depending on the evolution of the presence and degree of fatigue in the last twelve weeks. The Pearson Chi-squared test will be used for this purpose (or Fisher's exact test for 2x2 tables or likelihood ratio test for mxn tables, if necessary).

- Patient diary data (weekly): the distribution of patient frequencies will be presented according to the following habits:
  - Napping
    - Every day
    - Weekend and/or holidays
    - Sporadically, between 2 or 6 days
    - Has not taken a nap any day

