    - Number of dose changes received
      - 1 change \_ New dose
        - Sunitinib 50 mg 4/2 regimen
        - Sunitinib 50 mg 2/1 regimen
        - Sunitinib 37.5 mg 4/2 regimen
        - Sunitinib 37.5 mg 2/1 regimen
        - Sunitinib 25 mg 4/2 regimen
        - Sunitinib 25 mg 2/1 regimen
        - Pazopanib 800 mg/24 hours continuous
        - Pazopanib 400 mg/24 hours continuous
        - Sorafenib 400 mg/24 hours continuous
        - Sorafenib 400 mg/12 hours continuous
      - 2 changes\_ New dose
        - Sunitinib 50 mg 4/2 regimen
        - Sunitinib 50 mg 2/1 regimen
        - Sunitinib 37.5 mg 4/2 regimen
        - Sunitinib 37.5 mg 2/1 regimen
        - Sunitinib 25 mg 4/2 regimen
        - Sunitinib 25 mg 2/1 regimen
        - Pazopanib 800 mg/24 hours continuous
        - Pazopanib 400 mg/24 hours continuous
        - Sorafenib 400 mg/24 hours continuous
        - Sorafenib 400 mg/12 hours continuous
  - **Treatment interruptions:** the absolute and relative frequency of patients who have interrupted the treatment since the last cycle will be given. In

the sub-population of patients with treatment interruptions, their frequency distribution will be presented according to:

- Number of treatment interruptions
  - 1
  - 2
  - 3
  - 4 •
  - 5 •
  - ...
- Total calculation of days of treatment interruption
  - <7 days
  - 7-14 days
  - >14 days

In order to study the evolution of patients in terms of the presence of AEs (HFS and fatigue), patient habits in terms of daytime rest, aerobic physical exercise and taking medication, paired data comparisons will be performed between each one of the visits with the results of the previous visit, as well as of each one of the visits with regard to the results presented at the baseline visit, using, for this purpose, the non-parametric sign tests for categorical variables or the McNemar test in the case of dichotomous variables. In order to ascertain whether there is a significant evolution in the score obtained on the FACIT Fatigue scale throughout the study, comparisons of paired data will be performed for each one of the assessments with regard to the baseline value and with regard to the

previous evaluation using the Student t-test for paired data or the non-parametric Wilcoxon test, as appropriate.

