#### 9 LIST OF TABLES AND TABLE OF CONTENTS

Table/Graph number			Table/Graph title					
1.			Included and evaluable population					
2.			Descriptive analysis					
	.1		Demographic and disease information					
		.1	Age					
		.2	Time from diagnosis and from the advanced diagnosis of the disease					
		.3	Gender					
		.4	ECOG at time of diagnosis, Heng prognostic criteria and site of metastasis					
		.5	Histological type					
		.6	Smoking					
	.2		Dosage and treatment regimen of tyrosine kinase with which the patient begins treatment					
3.			Analysis of evolution					
	.1		Presence of palmar-plantar erythrodysesthesia of any grade (month 3, month 6, month 9)					
		.1	Association between medication intake habits and evolution of hand- foot syndrome (every three months)					
		.2	Association between dose changes and evolution of hand-foot syndrome (every three months)					
		.3	Association between dose, treatment regimen received and the evolution of hand-foot syndrome (every three months)					
		.4	Association between temporary treatment interruptions and evolution of hand-foot syndrome (every three months)					
	.2		Presence of fatigue of any grade (baseline, month 3, month 6, month 9)					
		.1	Association between daytime rest habit and fatigue evolution (every three months)					
		.2	Association between daytime physical exercise and fatigue evolution (every three months)					
		.3	Association between daytime medication-taking habits and fatigue evolution (every three months)					
		.4	Association between daytime dose changes and fatigue evolution (every three months)					
		.5	Association between doses, daytime treatment regimen and fatigue evolution (every three months)					

CT24-GSOP-SD-GL04 NI Study SAP Template; Template Version 1.0, Effective 31-Dec-2013 Page 23 of 29

PFIZER CONFIDENTIAL

	.6	Association between temporary daytime interruptions and fatigue evolution (every three months)
	3	Data from the patient diary
	.1	Daytime rest (weekly)
	.2	Physical exercise (weekly)
	.3	Has taken the medication (weekly)
•-	4	Quality of life (FACIT_Fatigue) (every six weeks)
	.1	Association between daytime habit and evolution on the Facit_Fatigue (every six weeks)
	.2	Association between daytime physical exercise and evolution on the Facit_Fatigue (every six weeks)
	.3	Association between daytime medication-taking habits and evolution on the Facit_Fatigue (every six weeks)

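### The hand-foot syndrome paragraph of SAP 8.2.3 tests within-patient change with chi-square tests of independence, in conflict with the paired tests prescribed later in the same section

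*SAP*

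**What the plan says.** The HFS paragraph of SAP 8.2.3 states that, at months 6 and 9, "a study will be performed to ascertain whether significant changes have occurred in the presence and the grade of the HFS". The comparison is "with regard to the previous visit, defined as (improved, maintained or worsened", so each patient is set against his or her own earlier status. The next sentence reads "The Pearson chi-squared test will be used for this purpose (or Fisher's exact test for 2x2 tables", with the likelihood-ratio test for larger tables.

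Three other places bear on this:

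- SAP 8.1 describes the same family of tests for the effect of administration time, napping, interruptions and dose reductions on fatigue and HFS: "independent samples will be compared using Pearson's chi-square test".
- The closing paragraph of SAP 8.2.3 covers the evolution of adverse events and names HFS. It says "paired data comparisons will be performed between each one of the visits with the results of the previous visit", and likewise against baseline, "using, for this purpose, the non-parametric sign tests for categorical variables or the McNemar test in the case of dichotomous variables".
- SAP section 9 lists four HFS association tables (3.1.1 to 3.1.4: medication intake, dose changes, dose and regimen, interruptions), for example "Association between dose changes and evolution of hand-foot syndrome (every three months".

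**The concern.** Whether HFS changed between two visits in the same patients is a paired question. A test of independence does not answer it, whichever table is used, and the SAP defines no table.

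- **Previous visit by current visit.** The null hypothesis is that status now is unrelated to status before. Rejection means that the same patients tend to keep HFS. It carries no information on whether HFS became more or less frequent.
- **Visit by status, both visits stacked.** The null hypothesis is the right one, but each patient is counted twice as if independent. With positive within-patient correlation the test is over-conservative.

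A reader of the study report could therefore be told that HFS changed significantly at month 6 or 9 when patients merely still had it. Because the closing paragraph of 8.2.3 also applies, the report could carry two contradictory p-values for one question.

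**Working it through.** The plan states no figure on this point, so there is nothing to reproduce. The check has two parts.

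**1. What the chi-square sentence refers to.** In the fatigue and FACIT-Fatigue paragraphs of SAP 8.2.3, a sentence on seeking associations with habits and dosing stands between the change sentence and the chi-square sentence, so chi-square there has a sensible object. The HFS paragraph has no such sentence, and its only stated purpose is change from the previous visit. Since section 9 nevertheless lists four HFS association tables, an association sentence was probably dropped. A goodness-of-fit reading (improved, maintained, worsened) does not fit either, because the text speaks of 2x2 and larger two-way tables.

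**2. What happens if the sentence is followed.**

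*Inputs from the SAP:* 100 patients and 5% discontinuation (section 5.1), giving 100 × 0.95 = 95; significance level 0.05 (section 4; two-sided assumed). *Assumed, because the documents give no HFS rate by visit:* prevalence, correlation between visits and number evaluable.

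*Formulas.* With a = HFS at both visits, b = previous only, c = current only, d = neither, and N = a+b+c+d:

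- Pearson on previous by current: X² = N(ad − bc)² / [(a+b)(c+d)(a+c)(b+d)], 1 df.
- Exact McNemar: two-sided binomial test of min(b, c) out of b + c with probability ½.

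*Worked tables, N = 95:*

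- No net change, persistent HFS: a=20, b=8, c=8, d=59, so 28/95 at both visits. X² = 95 × (1180 − 64)² / (28 × 67 × 28 × 67) = 33.62, p = 6.7×10⁻⁹. McNemar, 8 against 8: p = 1.00.
- Real rise, visits unrelated: a=6, b=9, c=32, d=48, so 15/95 to 38/95. ad − bc = 288 − 288 = 0, X² = 0, p = 1.00. McNemar, 9 against 32: p = 0.0004.
- Real rise, persistent HFS, visits stacked: a=20, b=2, c=12, d=61, so 22/95 to 32/95. Stacked chi-square p = 0.11. McNemar, 2 against 12: p = 0.013.

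*Simulation of presence* (correlated latent normals cut at the prevalence, 20,000 runs per setting, uncorrected Pearson, exact McNemar). Rejection rates at n = 80:

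| Scenario | Latent correlation | Cross-table chi-square | Stacked chi-square | McNemar |
|---|---|---|---|---|
| 30% at both visits | 0.5 to 0.7 | 81% to 99% | 1% to 2% | 3% |
| 30% at both visits | 0 to 0.2 | 5% to 20% | 4% to 5% | 3% |
| 30% to 50% | 0.5 to 0.7 | 82% to 99% | 77% to 80% | 83% to 92% |
| 30% to 50% | 0 to 0.2 | 5% to 20% | 73% to 75% | 68% to 74% |
| 30% to 45% | 0.5 to 0.7 | 82% to 99% | 50% | 58% to 70% |

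With no net change, over prevalence 20% to 50%, n = 60 to 95 and correlation 0.5 to 0.7, the cross-table test rejects in 61% to over 99% and McNemar in 2% to 3%.

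*Simulation of grade 0 to 3* (assumed 70/15/10/5% at both visits, n = 80, correlation 0.5 to 0.7, 4,000 runs): Pearson 82% to 99%, likelihood ratio 68% to 97%, exact sign test 3%. A repeat run agreed within about two percentage points.

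The cross-table rate depends on the correlation and hardly at all on whether HFS changed: compare the first and third rows.

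**The case against.** The strongest reply is that the SAP, read as a whole, already gets this right. The closing paragraph of 8.2.3 names HFS and prescribes paired tests, 8.1 ties the chi-square family to independent samples, and section 9 lists HFS association tables where chi-square on improved, maintained or worsened by habit or dosing is legitimate. Neither the previous-by-current table nor the stacked table is listed, so the high rejection rates arise only if an analyst builds one of them. Rejection on a cross-table is also a correct rejection of independence, and misleads only when labelled as change. The study is descriptive and HFS is a secondary objective.

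Much of this is fair, and it limits the consequence. It does not remove the fault: the HFS paragraph assigns the test to change in plain terms, the later paragraph does not withdraw it, and a programmer working from the HFS paragraph would apply that very label.

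Three qualifications stand:

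- At correlations of 0 to 0.2 the no-change cross-table rate is only 5% to 20%, so the large figures need persistence between visits.
- Fisher's test, allowed for 2x2 tables, lowers the figure somewhat in sparse tables (20% prevalence, n = 60, correlation 0.5: 53% against 61% for Pearson). The direction is unchanged.
- The closing paragraph speaks of the presence of adverse events, so the conflict is explicit for presence and only implied for grade. SAP 8.1 also assigns a Wilcoxon test to inter-visit quality of life, and section 6 defines HFS-related quality of life by the CTCAE score, so a second paired test for grade may be in play.

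**Conclusion.** The concern holds. SAP 8.2.3 gives two incompatible tests for change in HFS from the previous visit, and the one in the HFS paragraph does not test change. Used on a previous-by-current table with moderate to strong persistence, it would declare a change in most studies where there is none, and it gives nearly the same rejection rate when there is one. Used on stacked visits, it errs towards missing change. All rates rest on assumed prevalence, correlation and sample size; that a test of independence does not test change rests on none of them. The damage is limited to the p-values for visit-to-visit HFS change, a secondary objective. HFS frequencies and grades by visit, and the paired t or Wilcoxon comparison of the FACIT-Fatigue score, are unaffected. It should be corrected before the analysis is programmed.

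**What to change.** In the HFS paragraph of SAP 8.2.3:

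1. Replace the chi-square sentence for visit-to-visit change with a reference to the paired tests in the closing paragraph of that section: McNemar for presence, sign test for grade.
2. Add the missing sentence on HFS associations, and restrict chi-square, Fisher and likelihood-ratio tests to the four tables 3.1.1 to 3.1.4 in section 9.
3. State in the closing paragraph that it covers HFS grade as well as presence, and say in 8.1 whether the Wilcoxon test is meant for HFS grade, so that only one paired test applies.

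In the fatigue paragraph, at most a clause is needed saying that chi-square applies to the associations only. The cost is one SAP edit: no new data, and no test that the SAP does not already name.

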#### SECONDARY OBJECTIVES

- 1) Quality of life in patients with palmar-plantar erythrodysaesthesia (hand-foot syndrome).
- 2) To assess the following adverse events according to version 4 of the CTCAE (Common Terminology Criteria for Adverse Events): any grade of fatigue and HFS.
- 3) To study what role aerobic exercise (walking quickly, running, swimming, playing tennis, dancing and/or riding a bike) plays in the onset of fatigue before starting and during treatment.
- 4) To evaluate what impact the time of day of drug administration, napping, temporary treatment breaks and dose reductions have on controlling fatigue and hand-foot syndrome.
- 5) Time to Treatment Failure (TTF), defined as the time from the start of treatment with a tyrosine kinase inhibitor to tumour progression, treatment discontinuation for any reason or death from any cause.
- 6) Progression-Free Survival (PFS) (median): time from the start of treatment with a tyrosine kinase inhibitor to tumour progression or death from any cause.
- 7) Objective Response Rate according to RECIST version 1.1.

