## 4 HYPOTHESIS TESTING

The statistical significance value is set to p<0.05 The SPSS statistical package, V19.0 or later will be used.

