#### 5 ANALYSIS POPULATION

#### 5.1 FULL ANALYSIS SET

Plans are to include 100 patients in the study to receive first-line treatment over the course of 18 months at 35 sites.

This is a descriptive study; therefore, a specific number of patients is not required to calculate the sample size.

In order to study the fatigue-related quality of life of patients who are taking a tyrosine kinase inhibitor, evaluated using the validated 13-item FACIT-Fatigue scale for patients with metastatic renal cancer on Spanish, the inclusion of 100 patients with metastatic renal carcinoma who are about to receive first-line treatment with a tyrosine kinase inhibitor and who meet the screening criteria of the study is proposed.

This sample size will allow us to estimate percentages of patients with fatigue (severe/non-severe) during follow-up, with a 95% level of significance and an estimated proportion of 10%, assuming a discontinuation rate of 5%.

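### HFS and CTCAE-fatigue evolution is tested against dose changes and interruptions without conditioning on toxicity at the previous visit, so a measure with no effect can look beneficial or harmful

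*SAP*

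**What the plan says.** SAP 8.2.3 assesses, at months 6 and 9, "the presence and the grade of the HFS with regard to the previous visit, defined as (improved, maintained or worsened". At months 3, 6 and 9 it assesses change "in the grade of fatigue with regard to the previous visit, defined as (improved, maintained or worsened". For fatigue, the same section relates evolution in presence and degree over the last twelve weeks to habits, dose and schedule changes, interruptions and days of interruption. It uses Pearson's chi-squared, Fisher's exact or likelihood ratio tests.

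For HFS, the matching associations are planned in SAP 8.1 and in the table list in SAP 9, for example "Association between temporary treatment interruptions and evolution of hand-foot syndrome (every three months". The tables at issue are 3.1.2 and 3.1.4 (HFS) and 3.2.4 and 3.2.6 (fatigue), covering dose changes and interruptions.

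They serve secondary objective 4, the impact that "temporary treatment breaks and dose reductions have on controlling fatigue and hand-foot syndrome". SAP 4 adds: "The statistical significance value is set to p<0.05".

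SAP 8.2.3 limits the grade distributions to patients who have the toxicity. It states no such limit for the evolution analysis and gives no rule for a patient at grade 0 on both occasions.

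**The concern.** With three classes and no restriction, a patient with no toxicity at either visit can only be maintained. A patient whose grade 2 toxicity persisted gets the same class. A patient at grade 0 can stay or worsen but never improve. At the other end, grade 3 HFS cannot worsen on the 1 to 3 scale.

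This matters because breaks and reductions are not given at random. The background in both documents reports that 38% of patients interrupted and 50% reduced dose in the pivotal sunitinib trial, and attributes reductions and interruptions to adverse effects. Toxicity therefore influences both who receives the measure and which outcome classes are open to the patient. An unadjusted cross-tabulation picks up that shared cause. Objective 4 could then be answered with a significant association that says nothing about whether the measure controls toxicity.

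**Working it through.** **Figures in the plan.** SAP 5.1 states: "Plans are to include 100 patients in the study". With 5% discontinuation about 95 remain. At the assumed proportion of 10%, the 95% half-width is 1.96 × √(0.10 × 0.90 / 95) = 6.0 percentage points. The plan gives no target half-width and no calculation for the association tests, so there is no figure to reproduce for them.

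**Assumptions.** The documents give no grade-transition rates, no break rates by grade and no any-grade HFS rate (only 9% at grade 3-4). The following are assumed: 85 patients, of whom q = 30% have HFS at the previous visit. Of these, 35% improve, 50% stay and 15% worsen. Of unaffected patients, 15% develop HFS. The break has no effect.

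**Case A: breaks depend on toxicity at the previous visit.** Let b1 and b0 be the break probabilities in affected and unaffected patients.

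- Share affected among those with a break = q·b1 / [q·b1 + (1−q)·b0].
- Share affected among those without = q(1−b1) / [q(1−b1) + (1−q)(1−b0)].
- Share improved = share affected × 0.35.

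| b1 vs b0 | Affected: break / no break | Improved: break / no break | p<0.05, all patients |
|---|---|---|---|
| 50% vs 10% | 68.2% / 19.2% | 23.9% / 6.7% | 50% |
| 40% vs 15% | 53.3% / 23.2% | 18.7% / 8.1% | 24% |
| 30% vs 20% | 39.1% / 27.3% | 13.7% / 9.5% | 9% |

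First row: 0.15 / (0.15 + 0.07) = 0.682 and 0.682 × 0.35 = 0.239. The last column is from simulation (3,000 runs per setting, Pearson chi-squared on a 2 × 3 table). Among affected patients only, rejection was about 4-5%. In the first row, 99.7% of rejections favoured breaks. The maintained class is 0.70 × 0.85 = 0.595 without HFS at either visit plus 0.30 × 0.50 = 0.150 with unchanged HFS, so 0.595 / 0.745 = 80% of it never had HFS at either visit.

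A separate set of simulations used 95 patients, 20-60% affected, and breaks in 50-60% of affected and 16-33% of unaffected patients. Rejection was 13-51% pooled and 4-5% among affected patients. The settings with 50-60% affected, within the 50-75% asthenia range in the background, gave 20-51% pooled. With breaks unrelated to previous toxicity, it was 4.7%.

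**Case B: breaks respond to toxicity arising within the interval.** Assume 30% affected; 40% of these improve, 45% stay and 15% worsen; 15% of unaffected patients develop toxicity. Breaks occur in 70% of those who worsen, 40% of other affected patients and 25% of those free of toxicity throughout.

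- Worsened with a break: 0.15 × 0.70 = 0.105.
- All with a break: 0.105 + 0.30 × 0.85 × 0.40 + 0.70 × 0.85 × 0.25 = 0.105 + 0.102 + 0.149 = 0.356.
- Share worsened: 0.105 / 0.356 = 29.5% with a break; 0.045 / 0.644 = 7.0% without.

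The pooled test rejects in 80% of runs here and in 75-96% across four such settings. In 98-100% of those rejections the break group has more worsening. Restriction to affected patients leaves 5%, 14%, 14% and 36%.

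**Does restriction to grade 1 or higher suffice in Case A?** Not if grade still varies. With assumed break probabilities of 20/60/90% and improvement of 20/45/70% at grades 1/2/3, and no effect of the break, the test among affected patients rejects in 11% of runs at 30% prevalence and 23% at 60%.

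**The case against.** A reader might infer that the tables will show breaks and dose changes as effective whatever they do, and that this follows from the coding alone. The documents support neither step. When breaks are unrelated to previous toxicity, rejection stays near 5%; the problem is confounding by earlier toxicity in an unadjusted comparison, to which the coding contributes. The direction is also open. The twelve-week window does not require the break to come before the grade change, and a break that answers new toxicity looks harmful.

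The pooling is inferred from silence. The grade lists start at grade 1 and are given for affected patients, so one could read the evolution analysis as confined to them too. That reading is weakened because the HFS sentence and the fatigue association both name presence as well as grade. The fair statement is that the denominator and the grade 0 rule are undefined.

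Nor is the study blind to the difference between absent and persistent toxicity. SAP 8.2.3 reports any-grade frequency and grade distribution at each visit, with paired sign and McNemar tests, and for fatigue it also relates the measures to FACIT-Fatigue change. These limit the damage to the association tables but do not repair them. The mechanism is not shown for the tables on napping, exercise, medication timing and regimen.

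Calling the study descriptive does not answer the point, since the SAP sets a significance level and seeks significant associations.

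**Conclusion.** The concern holds as a failure to define the denominator and to condition on previous grade in Tables 3.1.2, 3.1.4, 3.2.4 and 3.2.6. As written, a dose change or interruption with no effect can produce a significant association well above 5%: apparent benefit if it follows toxicity already present at the previous visit, apparent harm if it responds to toxicity arising in the interval. The rates of 9-50% (HFS, Case A) and 75-96% (Case B) are illustrative. They rest on assumed prevalence, transition rates and break rates, and Case A falls to about 5% if breaks do not depend on toxicity. The existence of the problem needs only that dependence, which the background describes. It affects a secondary objective and should be corrected before analysis.

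**What to change.** In SAP 8.2.3 and the four tables:

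1. Analyse new onset (yes/no) only in patients at grade 0 at the previous visit, and improved/unchanged/worsened only in patients at grade 1 or higher. Give absent at both visits its own row.
2. Stratify by or adjust for previous grade. An ordinal model of current grade with previous grade as covariate is preferable, because the grade 1 or higher group still mixes grades; splitting the groups alone is not equivalent.
3. Count only interruptions and dose changes that precede the assessed grade change.
4. Report the associations as descriptive, with intervals.

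Items 1, 2 and 4 need only SAP wording and table shells, since grades are already planned at each visit. For item 3, Protocol 7.3 records the cycle of each dose change and interruption. The documents available do not show whether the CRF dates each grade change, so this should be checked. The price is smaller denominators and wider intervals: at 30% prevalence, 0.30 × 85 is about 25 patients affected by HFS, too few to support much testing.
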